5.3 LIFESTYLE CONSIDERATIONS

No restrictions are required in this study.

5.4 SCREEN FAILURES

Screen failures are defined as participants who consent to participate in the clinical study but are not subsequently enrolled. A minimal set of screen failure information is required to ensure transparent reporting of screen failure participants to meet the Consolidated Standards of Reporting Trials publishing requirements and to respond to queries from regulatory authorities. Minimal information includes demography, screen failure reasons, eligibility criteria, and any serious adverse event (SAE).

Individuals who do not meet the criteria for participation in this study (screen failure) may be rescreened. Rescreened participants should be assigned a new participant number for every screening/rescreening event.

There is no requirement for a waiting period between the screen failure date and the rescreening date. The interactive voice/web response system (IVRS/IWRS) report will flag rescreened participants. The Investigator will obtain information about subsequent scheduled visits via the IVRS/IWRS, which will be available 24 hours a day.

Participants who fail screening during the Screening Period may be rescreened for study eligibility only once for the following criteria:

- They do not meet the inclusion criterion of having a weekly average NC symptom severity score >1 at Visit 2.
- They have an acute illness such as acute sinusitis, nasal infection, or upper respiratory infection (E 01). These participants can be rescreened only after complete resolution of symptoms.
- They have taken one of the prohibited treatments listed in [Section 6.8](#) during the Screening Period.

Participants who are rescreened must sign a new consent form, and all of the Visit 1 procedures must be repeated (refer to [Section 10.1.3](#) for further instructions related to rescreening) unless a prior assessment is performed within the time frame permitted prior to study entry or the Visit 1

baseline CT scan of sinuses is performed. Participants with positive test results for HIV or hepatitis will not be allowed to rescreen.

All participants must fulfill all eligibility criteria before enrollment into the study; no waiver will be allowed for enrollment.

If certain dynamic laboratory tests do not meet the eligibility criteria, these laboratory assessments may be repeated, at the discretion of the Investigator, if the results are judged to be likely to return to acceptable range for study inclusion within the Screening Visit window.

For participants who do not fulfill other exclusion criteria, rescreening should be discussed with the Sponsor. In all cases, a given participant can only be rescreened once.

5.5 CRITERIA FOR TEMPORARILY DELAYING SCREENING

During a regional or national emergency declared by a governmental agency, if the site is unable to adequately follow protocol-mandated procedures, contingency measures are proposed in Appendix 7: Contingency measures for a regional or national emergency that is declared by a governmental agency ([Section 10.7](#)) should be considered for screening.

6 STUDY INTERVENTION(S) AND CONCOMITANT THERAPY

Study intervention is defined as any investigational intervention(s), marketed product(s), placebo, or medical device(s) intended to be administered to a study participant according to the study protocol.

6.1 STUDY INTERVENTION(S) ADMINISTERED

Approximately 25 participants will be enrolled and will be assigned to study intervention as described below:

- Dupilumab 300 mg q2w up to Week 24 (all participants)
- Dupilumab 300 mg q4w after Week 24 (participants who have stable disease at Week 24)
- One injection of 300 mg q2w after Week 24 (participants who cannot achieve stable disease)

For participants who have stable disease (NPS improvement from baseline to both Weeks 16 and 24 ≥ 2 points), the dosing interval can be changed from q2w to q4w at the discretion of the Investigator at Week 24. Participants who proceed from the q2w regimen to the q4w regimen will receive the q4w regimen up to Week 48 and will not be permitted to return to the q2w regimen during this study. Other participants will receive q2w regimen up to Week 50. All participants will be followed up to Week 52.

At Visit 2, the Investigator (or designee) will prepare and perform the first IMP injection in front of the participant (or parent/LAR/caregiver). The IMP will be administered following clinic procedures. Participants will be monitored at the study site for at least 30 minutes after the injection for signs of hypersensitivity reaction.

After the second dose of IMP, home administration of IMP q2w (by participant, caregiver, or health care professional) is possible if the participant (or caregiver) has been appropriately trained at the study site. Training must be documented when it is completed successfully, and training injections must be recorded in the participant's study file. In case of emergency (eg, natural disaster, pandemic), different training methods (eg, training remotely with instruction provided by phone) can be performed (and will be documented in the participant's study file). When IMP is administered at home, the participants must be advised by the site staff to self-monitor for potential signs and symptoms that may suggest a hypersensitivity reaction for at least 30 minutes after administration.

If the participant (or caregiver) is unable or unwilling to administer IMP, arrangements must be made for qualified site personnel and/or healthcare professionals to administer IMP for the doses that are not scheduled to be given at the study site. If the participant or caregiver(s) do not become comfortable with injecting the IMP at home or if the Investigator determines that participant (or caregiver) administering an injection at home is not appropriate, injections can be performed at the site by way of unscheduled visits.

Subcutaneous injection sites should be alternated among the 4 quadrants of the abdomen (avoiding the navel and waist areas), the upper thighs, and the upper arms, such that the same site is not injected twice consecutively. Injection in the upper arms can be done only by a trained person (caregiver trained by Investigator or designee) or health care professional but not the participants themselves.

Post-trial access to IMP will not be provided.

Table 2 - Overview of study interventions administered

Arm name	Dupilumab
Intervention name	Dupilumab 300 mg
Type	Biological
Dose formulation	A 150 mg/mL dupilumab solution in a prefilled syringe to deliver 300 mg in 2 mL
Unit dose strength(s)	300 mg
Dosage level(s)	300 mg q2w or q4w ±3 days
Route of administration	Subcutaneous
Use	Experimental
IMP or NIMP	IMP
Packaging and labeling	One glass prefilled syringe packed in a participant kit box. Both the glass prefilled syringe and the box will be labeled as required per country requirement.
Former names	Dupixent
Abbreviation: IMP: investigational medicinal product; NIMP: noninvestigational medicinal product; q2w: every 2 weeks; q4w: every 4 weeks	

The IMP may be supplied at the site or from the Investigator, site, or Sponsor to the participant via a Sponsor-approved courier company where allowed by local regulations and agreed upon by the participant.

Detailed instructions for transport, storage, preparation, and administration of IMP are provided to the participants. For doses that are not given at the study site, participants will complete a paper dosing diary to document compliance with self-injection (or caregiver injection) of IMP, location of injection, and any symptoms. The diary will be kept as source data in the participant's study file.

For a regional or national emergency declared by a governmental agency that results in travel restrictions, confinement, or restricted site access, contingency measures are included in Appendix 7: Contingency measures for a regional or national emergency that is declared by a governmental agency ([Section 10.7](#)).

6.1.1 Packaging and labeling

Dupilumab 300 mg will be supplied at each visit as glass prefilled syringes packed in one participant kit box. The number of kits to be supplied to each participant at each visit is based on the Investigator's instruction.

The content of the labeling is in accordance with the local regulatory specifications and requirements.

6.2 PREPARATION/HANDLING/STORAGE/ACCOUNTABILITY

6.2.1 Storage and handling

1. The Investigator or designee must confirm that appropriate temperature conditions have been maintained during transit for all study intervention received and that any discrepancies are reported and resolved before use of the study intervention.
2. Only participants enrolled in the study may receive study intervention, and only authorized site staff may supply it. At site, all study interventions must be stored in a secure, environmentally controlled, and monitored (manual or automated) area in accordance with the labeled storage conditions with access limited to the Investigator and authorized site staff.
3. The Investigator, institution, or the head of the medical institution (where applicable) is responsible for study intervention accountability, reconciliation, and record maintenance (ie, receipt, reconciliation, and final disposition records).

It is the responsibility of the Investigators to inform the participants regarding the mandatory storage requirements for the IMP. No temperature monitoring will be performed at the participants' homes.

6.2.2 Responsibilities

Any quality issue noticed with the receipt or use of an IMP (deficiency in condition, appearance, pertaining documentation, labeling, expiration date, etc) must be promptly notified to the Sponsor. Some deficiencies may be recorded through a complaint procedure (see [Section 8.3.8](#)).

A potential defect in the quality of IMP may be subject to initiation of a recall procedure by the Sponsor. In this case, the Investigator will be responsible for promptly addressing any request made by the Sponsor, in order to recall the IMP and eliminate potential hazards.

Under no circumstances will the Investigator supply IMP to a third party (except for direct-to-patient [DTP] shipment, for which a courier company has been approved by the Sponsor), allow the IMP to be used other than as directed by this clinical study protocol, or dispose of IMP in any other manner.

6.2.3 Treatment accountability and compliance

The Investigator or designee will keep accurate records of the quantities of the IMP dispensed and returned, used and unused by each participant.

- Proper recording of treatment kit numbers as required on the appropriate e-CRF page for accounting purposes.
- All medication treatment kits (whether empty or unused) are returned by the participant at each visit when a treatment dispensing is planned and at the EOT/EOS Visit.
- The completed patient diary (returned to the site at each visit), returned IMP treatment kit boxes, used and unused, along with any unused prefilled syringes will be used for drug accountability purposes. Participants will also return used prefilled syringes to the site in a sharps container.
- The Investigator (or designee) will track treatment accountability/compliance by diary and by counting the number of used and unused treatment kits and syringes and will complete the appropriate page of the patient treatment log.
- The monitor in charge of the study will then check the data entered on the IMP administration page by comparing them with the IMPs that have been retrieved and the patient treatment log forms. Reconciliation will occur with the paper diary as appropriate depending on the study visit/period.

6.2.4 Return and/or destruction of treatments

Whenever possible, all partially used, used, or unused IMP provided by the Sponsor will be destroyed on-site according to the standard practices of the site. A detailed treatment log of the destroyed IMP supplied by the Sponsor will be established with the Investigator (or the pharmacist) and countersigned by the Investigator and the monitoring team. The Investigator will not destroy any IMP supplied by the Sponsor unless the Sponsor provides written authorization. When destruction at the site cannot be performed, all IMP supplied by the Sponsor will be retrieved by the Sponsor. A detailed treatment log of the returned IMP supplied by the Sponsor will be established with the Investigator (or the pharmacist) and countersigned by the Investigator and the monitoring team.

6.3 MEASURES TO MINIMIZE BIAS: RANDOMIZATION AND BLINDING

This is an open-label, single-arm study; randomization and blinding will not be implemented.

6.4 STUDY INTERVENTION COMPLIANCE

- Methods used by the Investigator or his/her delegate to ensure that the IMP was administered

- IMP accountability:
 - Intervention units are returned by the participant at each visit. In case of DTP process, the intervention units can be returned by the carrier (if defined in the contract).
 - The Investigator counts the number of prefilled syringes remaining in the returned packs and fills in the intervention log form.
 - The Investigator records the dosing information on the appropriate page(s) of the e-CRF.
 - The monitor in charge of the study then checks the e-CRF data by comparing them with the IMP that he/she has retrieved and the intervention log forms.
 - Proper placement of tear-off label for accounting purposes.

When participants are dosed at the site, they will receive study intervention directly from the Investigator or designee under medical supervision. The date and time of each dose administered in the clinic will be recorded in the source documents and recorded. The dose of study intervention and study participant identification will be confirmed at the time of dosing by a member of the study site staff other than the person administering the study intervention.

When participants self-administer study intervention(s) at home, compliance with study intervention will be assessed at each visit. Compliance will be assessed by patient diary (returned to the site at each visit) and by returned IMP treatment kit boxes, both used and unused, along with any unused prefilled syringes during the site visits and documented in the source documents and relevant form. Deviation(s) from the prescribed dosage regimen should be recorded (refer to [Section 6.2.3](#) for details).

A record of the quantity of IMP dispensed to and administered by each participant must be maintained and reconciled with study intervention and compliance records. Intervention start and stop dates, including dates for intervention delays and/or dose reductions, will also be recorded.

6.5 DOSE MODIFICATION

For participants who have stable disease (NPS improvement from baseline to both Weeks 16 and 24 is ≥ 2 points), the dosing interval can be changed from q2w to q4w at the discretion of the Investigator at Week 24. Participants who proceed to the dosing interval from q2w to q4w will not be permitted to return to the q2w regimen during this study. The maximum dose will not exceed dupilumab 300 mg q2w.

However, any dose reduction is not allowed other than above.

6.5.1 Retreatment criteria

Not applicable.

6.6 CONTINUED ACCESS TO INTERVENTION AFTER THE END OF THE STUDY

Post-trial access to study medication will not be provided.

6.7 TREATMENT OF OVERDOSE

For this study, any dose of dupilumab greater than twice the intended dose during an interval of less than 11 days will be considered an overdose.

No antidote is available for dupilumab. The Sponsor does not recommend specific treatment for an overdose. Symptomatic overdoses (serious or nonserious) are required to be reported as AE of special interests (AESI) (refer to [Section 8.3.6](#)).

In the event of an overdose, the Investigator should:

- Contact the Sponsor immediately.
- Evaluate the participant to determine, in consultation with the Sponsor, whether study intervention should be interrupted.
- Closely monitor the participant for any AE/SAE and laboratory abnormalities until dupilumab can no longer be detected systemically.
- Document appropriately in the e-CRF.

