8.3.1 Time period and frequency for collecting AE and SAE information

All AEs (serious or nonserious) will be collected from the signing of the ICF until the EOT/EOS Visit at the time points specified in the SoA ([Section 1.3](#)).

All SAEs and AESI will be recorded and reported to the Sponsor or designee immediately, and under no circumstance should this exceed 24 hours, as indicated in Appendix 3 ([Section 10.3](#)). The Investigator will submit any updated SAE data to the Sponsor within 24 hours of the data being available.

The Investigator should take appropriate measures to follow all AEs until clinical recovery is complete and laboratory results have returned to normal, until progression has been stabilized, or until death, in order to ensure the safety of the participants. This may imply that observations will continue beyond the last planned visit per protocol and that additional investigations may be requested by the monitoring team up to the time as noticed by the Sponsor.

The Investigators are not obligated to actively seek information on AEs or SAEs after conclusion of the study participation. However, if the Investigator learns of any SAE, including a death, at any time after a participant has been discharged from the study and he/she considers the event to be reasonably related to the study intervention or study participation, the Investigator must promptly notify the Sponsor.

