 - Symptomatic overdose (serious or nonserious) with IMP
 - An overdose (accidental or intentional) with the IMP is an event suspected by the Investigator or spontaneously notified by the participant and defined as at least twice the intended dose during an interval of less than 11 days. The circumstances (ie, accidental or intentional) should be clearly specified in the verbatim and symptoms, if any, entered on separate AE forms.

Of note, asymptomatic overdose has to be reported as a standard AE.

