10.1.6 Data quality assurance

- All participant data relating to the study will be recorded on e-CRF unless transmitted to the Sponsor or designee electronically (eg, laboratory data). The Investigator is

responsible for verifying that data entries are accurate and correct by electronically signing the CRF.

- Guidance on completion of e-CRFs will be provided in CRF Completion Guideline.
- The Investigator must maintain accurate documentation (source data) that supports the information entered in the e-CRF.
- The Investigator must permit study-related monitoring, audits, IRB review, and regulatory agency inspections and provide direct access to source data documents.
- Quality tolerance limits (QTLs) will be predefined in the Centralized Monitoring Plan to identify systematic issues that can impact participant safety and/or reliability of study results. These predefined parameters will be monitored during the study and important deviations from the QTLs and remedial actions taken will be summarized in the clinical study report.
- Monitoring details describing strategy (eg, risk-based initiatives in operations and quality such as Risk Management and Mitigation Strategies and Analytical Risk-Based Monitoring), methods, responsibilities, and requirements, including handling of noncompliance issues and monitoring techniques (central, remote, or on-site monitoring) are provided in separate study documents.
- The Sponsor or designee is responsible for the data management of this study including quality checking of the data.
- The Sponsor assumes accountability for actions delegated to other individuals (eg, Contract Research Organizations).
- Records and documents, including signed ICFs, pertaining to the conduct of this study must be retained by the Investigator for 25 years after the signature of the final study report unless local regulations or institutional policies require a longer retention period. No records may be destroyed during the retention period without the written approval of the Sponsor. No records may be transferred to another location or party without written notification to the Sponsor.

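### Protocol 6.7 and 8.3.6 set different overdose thresholds, so it is unclear whether the 6.7 steps apply to an exact double dose (600 mg)

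*Protocol*

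**What the plan says.** Protocol 6.7 gives the definition that governs what the site does: "any dose of dupilumab greater than twice the intended dose during an interval of less than 11 days will be considered an overdose". For an event that meets it, the Investigator is to contact the Sponsor at once, monitor the participant closely, document the event in the e-CRF, and carry out this review: "Evaluate the participant to determine, in consultation with the Sponsor, whether study intervention should be interrupted". The same section sends the reader to 8.3.6 for the reporting of symptomatic overdose.

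Protocol 8.3.6 lists symptomatic overdose among the AESIs and gives its own definition: "defined as at least twice the intended dose during an interval of less than 11 days". It adds that "asymptomatic overdose has to be reported as a standard AE".

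Four other provisions bear on the point:

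- Protocol 6.1, Table 2: the intended dose is 300 mg every 2 or 4 weeks, ±3 days, supplied as "One glass prefilled syringe packed in a participant kit box".
- Protocol 8.3.1: "All SAEs and AESI will be recorded and reported to the Sponsor or designee immediately, and under no circumstance should this exceed 24 hours".
- Protocol 6.4: "Deviation(s) from the prescribed dosage regimen should be recorded".
- SAP Table 9: symptomatic overdose is selected from two e-CRF answers, one for overdose and one for symptoms. No numerical threshold is given.

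**The concern.** The two definitions share the product, the reference dose and the time limit, and differ only in whether exactly double counts. That boundary is what one extra full syringe produces, and 6.1 allows home injection by the participant or a caregiver after the second dose. It is therefore a dosing error the protocol should expect.

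Two sites could each follow the protocol and act differently on the same event. A site working from 6.7 alone could treat 600 mg as outside its overdose steps. A site working from 8.3.6 would call it an overdose and could then apply them. Because 6.7 refers to 8.3.6, the text does not clearly exclude a double dose from those steps. It leaves the matter open.

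**Working it through.** No figure in the plan needs reproducing. The check compares the two rules at each possible syringe count and then tests the inclusive rule against the dosing window.

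**Step 1: thresholds.** Intended dose = 300 mg (Table 2), so twice the intended dose = 2 × 300 = 600 mg. Section 6.7 requires a total above 600 mg in under 11 days. Section 8.3.6 requires 600 mg or more in under 11 days.

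**Step 2: whole syringes given in under 11 days.**

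| Syringes | Total | Multiple | 6.7 (> 2) | 8.3.6 (≥ 2) |
|---|---|---|---|---|
| 1 | 300 mg | 300/300 = 1.0 | no | no |
| 2 | 600 mg | 600/300 = 2.0 | no | **yes** |
| 3 | 900 mg | 900/300 = 3.0 | yes | yes |

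The sections disagree at two syringes only. In whole syringes, the smallest overdose is 900 mg under 6.7 and 600 mg under 8.3.6.

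**Step 3: what is settled at 600 mg and what is not.**

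- Symptomatic: an AESI under 8.3.6, with the Sponsor told within 24 hours (8.3.1). Of the 6.7 steps, the explicit interruption review and close monitoring stay unclear.
- Asymptomatic: a standard adverse event (8.3.6), followed up like other adverse events (8.3.1), with the dosing deviation recorded (6.4). Immediate Sponsor contact, interruption review and close monitoring all stay unclear.

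**Step 4: does the inclusive rule catch permitted dosing?** The step 2 count adds up all doses inside the interval, so scheduled doses must be tested in the same way.

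- Nominal gap at every 2 weeks: 14 days.
- One dose 3 days early, its neighbour on time: 14 − 3 = 11 days. This is not under 11, so the rule is not triggered.
- One dose 3 days late, the next 3 days early: 14 − 3 − 3 = 8 days. The Schedule of Activities sets Week 2 at Day 15 ± 3 and Week 4 at Day 29 ± 3, so Day 18 and Day 26 are both in window, and 26 − 18 = 8.

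In the last case two compliant single doses total 600 mg in under 11 days. On a cumulative reading this already meets the 8.3.6 wording, and it would meet 6.7 too if 6.7 were aligned without an exception. The strict wording in 6.7 does not catch it.

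**The case against.** The strongest reply is that little is left uncovered. Section 8.3.6 governs reporting, 6.7 itself points there, syringes are counted and reconciled (6.2.3), and the Investigator may interrupt treatment for suspected adverse events (7.1.3). Section 6.7 recommends no specific treatment. Section 8.2.8 names 300 mg weekly as the highest dose level in dupilumab studies, so two 300 mg doses a week apart fall within a studied regimen. All of this stands and keeps the point minor. It does not tell a site whether the 6.7 steps apply at 600 mg.

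A second reply is that the inclusive wording could label compliant dosing as overdose. Step 4 shows that this is correct for visit-anchored doses. Table 2 does not say whether its ±3 days runs from the schedule or from the previous dose. If from the previous dose, the shortest gap is 11 days and the problem disappears, but the visit windows are tied to study day. This calls for an exception in the text. It is not a reason to keep two definitions.

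A reader might infer three stronger things that the documents do not support:

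- *Double doses escape safety reporting.* They do not. They are an AESI or a standard adverse event, and a recorded deviation.
- *The overdose line in the SAP safety table will be wrong.* Sites could answer the e-CRF item differently, but "Guidance on completion of e-CRFs will be provided in CRF Completion Guideline", and that guideline is not among the documents. It may already define the item.
- *The inclusive threshold was plainly intended.* The 11-day limit equals 14 − 3, which fits the inclusive rule, but the documents do not state which wording was meant.

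**Conclusion.** The protocol is wrong as written, in a small way and in a safety rule only. Its two overdose definitions conflict at exactly twice the dose, and an exact double dose of 600 mg falls in that gap. The main consequence is uncertainty over immediate Sponsor contact, interruption review and close monitoring after an asymptomatic double dose. Efficacy analyses and sample size are not touched.

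The comparison assumes full 300 mg syringes and counts the total given inside the interval. The documents give no dosing-error rate, so no frequency is claimed. The text should be corrected, but the conflict does not threaten the trial's conclusions.

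**What to change.** 1. In Protocol 6.7, replace *greater than twice* with *at least twice*, keeping the 11-day limit, so that it matches 8.3.6. The inclusive form is preferred because it covers a double injection and because 6.7 already relies on 8.3.6 for reporting.
2. In both sections, state that two scheduled single doses, each given within its permitted ±3-day window, are not an overdose even when they fall as little as 8 days apart.
3. Use the same definition for the e-CRF overdose item that feeds SAP Table 9, and check the completion guideline against it.

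The cost is modest but not nil. A few more dosing errors would trigger the 6.7 steps, including monitoring until the drug is no longer detectable, although 8.4 says pharmacokinetics are not evaluated. The change needs a protocol amendment or clarification. Under 10.1.1 an amendment goes to the IRB, and to the health authority if it is substantial. The amendment history (10.14) lists none to which it could be attached. Visits, sample size and planned analyses stay as they are.
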